1.2 Primary Study Endpoints

State the primary endpoints to be measured in the study.

Research typically has a primary objective or endpoint. Additional objectives and endpoints are secondary. The endpoints (or outcomes), determined for each study subject, are the quantitative measurements required by the objectives. Measuring the selected endpoints is the goal of a trial (examples: response rate and survival).

The primary outcomes of this study are 1) the effect of SABL on residents' agitation, other BPSD, affect, sleep and any side effects, 2) fidelity of SABL (e.g., lighting level on site and at individual level), and 3) feasibility of implementing SABL (e.g., acceptability, feasibility, appropriateness, time, and cost of implementing and maintaining the lighting).

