7.1 Study Design

Describe and explain the study design.

Aim 1: Pilot test the effect of SABL in reducing agitation in persons with dementia. This is a crossover, cluster randomized control trial to pilot test the effect of SABL in NHs. This design includes a 4-week intervention period and 2-week washout period. This design will allow for participants to act as their own control and thus reduce the needed sample size and strengthen the research rigor. The study procedures include five phases over 13 weeks. We will recruit a total sample of 40 nursing home residents with dementia and agitation from the 2 nursing homes, 20 residents from each nursing home. The two NHs will be randomly assigned into different sequences for intervention and control. Otherwise, the same study procedures will be

conducted simultaneously at the two NHs. During the daytime, participants will be guided and encouraged to spend time in the designated areas in the dining room and activity room for their meals and daily activities. For blinding prior to control period, we will perform installation procedures with non-SABL light bulbs. We will evaluate the effect of SABL on agitation, other BPSD, affect, and sleep, based on the actual lighting levels participants receive measured by personal light monitors. The study procedures include five phases: 1) baseline, 2) intervention, 3) post intervention/washout, 4) control, and 5) post control/washout. The sequence of intervention and control differs between the two NHs based on randomized assignment. Agitation and lighting will be measured at baseline and then once every two weeks throughout the study. We hypothesize that participants will show less agitation during and after SABL compared to baseline and control periods. We will also explore the intervention effect on other BPSD and affect and monitor adverse effects. **Aim 2: Evaluate the fidelity of the SABL delivery.** We will evaluate the fidelity of SABL delivery by measuring lighting intensity (lux) and CS levels in two ways: 1) on-site light measurements, and 2) a personal light monitor. The actual lighting data will be compared to the intended SABL design.

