Four strategies will be implemented to ensure the actual lighting condition the SABL delivers is as designed. First, SABL system has a pre-programmed 24-hour control schedule on illuminance settings to automatically maintain the target lighting dosage. The SABL include photosensors to measure the lighting every 10 minutes and will automatically adjust tunable LED lights through wireless communication to accommodate the daylight effect. Second, the wall-mounted photosensors can detect any problematic lighting events (e.g., <400lux or CS<0.3 during the day) in real-time and will trigger alerts to the research team for trouble shooting. Third, a comprehensive in field lighting measurement will be performed by the research team twice a week during the intervention and control periods to confirm the designed conditions and address any lighting system issues. Fourth, we will remotely monitor the lighting data from the personal light monitors and then analyze the daily data during the data collection week to detect any individual compliance issues and potential device or lighting problems.

The following will describe the installation of SABL system.

First, the SABL system will be installed in resident participants' bedrooms, and designated areas in the hallways, dining rooms, and activity rooms to cover areas that resident participants usually spend time with. Specifically, in the dining room and activity room, the lighting system will only cover the participating residents' tables and areas where they sit. Note that residents and staff typically only spend minimal time in hallways. As a check, prior to installation, the SABL system will be verified via the computer simulation in a lab setting to ensure it only covers the designed areas for participants.

Second, prior to the study, we will announce the general timeline of the study period and will post signs in the dining rooms and activity rooms to notify people that lighting interventions are taking place. While nonparticipants and staff are not restricted from entering the rooms with SABL lighting, they can opt out of the specific areas in the rooms with SABL if they prefer. Non-participating residents will be informed the research areas and the priority of the areas will be given to participants.

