- 1) Data extraction from CMS Nursing Home Compare Website (<https://www.medicare.gov/care-compare/>): Data on facility characteristics, including number of certified beds, ownership, quality rating, participation in Medicaid, staffing, COVID-related data is publicly available and can be accessed through the link provided above.
- 2) Chart reviews: Data on resident characteristics, including age, race, sex, diagnoses, level of cognitive impairment, current medication use, current listed comorbidity and physical function, BPSD in the past two weeks, pain in the past two weeks, current vision status, current hearing status, and other clinical conditions.
- 3) Surveys based on staff caregivers' reports: The surveys will be conducted on paper and in-person with researcher administering the survey to the staff caregiver for proxy report of residents' dementia stage, agitation, other BPSD, affect, and side effects.
- 4) Personal light monitor, LYS button, placed on individual resident participants to measure lighting intensity (lux) and CS levels participants receive.

There will be seven visits for data collection throughout the 13-week of the study: baseline visit (week 1) and six follow-up visits, every other week (weeks 3, 5, 7, 9, 11, 13). The procedures for each visit are as follows:

Baseline visit: Procedures 1 through 4.

Follow-up visits: Procedures 3 and 4.

For the procedure 4, the light monitor will be worn 7 days a week during the data collection weeks (week 1, 3, 5, 7, 9, 11, & 13).

Aim 2: We will evaluate the fidelity of SABL delivery by measuring lighting intensity (lux) and CS levels.

Data collection procedures will include the following:

- 1) on-site manual light measurements
- 2) personal light monitor, LYS button, placed on individual resident participants (same as the procedure 4 in aim 1).

The procedures will be conducted primarily on site at the nursing home facilities.

The procedure 1 will be conducted twice a week throughout the 13-week study period.

For the procedure 2, as mentioned in aim 1, the light monitor will be worn 7 days a week during the data collection weeks (week 1, 3, 5, 7, 9, 11, & 13).

Aim 3: Staff and Administrators

Data collection methods include the following:

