- 1) Surveys: Surveys will be administered to staff in-person and on paper to collect their characteristics (e.g., age, race, gender, education, & professional experiences) and their evaluation on the acceptability, feasibility, and appropriateness of the SABL lighting intervention.
- 2) Qualitative interviews: Staff's and administrators' inputs on the acceptability, feasibility, and appropriateness of the SABL lighting intervention.
- 3) We will also calculate the total hours and cost of installing and maintaining the SABL.

The procedures can be conducted either in person at the facility or via virtual conference (e.g., zoom). The procedure will be conducted in one visit scheduled in week 13.

Table 1. Intervention testing procedures and timeline.

Week		1	2	3	4	5	6	7	8	9	10	11	12	13
Study phases	NH A	Baseline	Intervention			Post intervention/washout			Control			Post control		
	NH B		Control			Post control/washout			Intervention			Post intervention		
Lighting		Usual light	I: SABL C: Usual light			Usual light			C: Usual light I: SABL			Usual light		
Data collection		Baseline, L&E		L&E		L&E		L&E		L&E		L&E		L&E

L=lighting measured via individual light monitor, E=effect outcomes (e.g., agitation, BPSD, affect, and sleep) and adverse effects

Table 2 Summary of Variables, Measures, and Data Collection.

Aim	Variables	Measures	Data collection methods	Timing
Aim 1	Facility characteristics	# of certified beds, ownership, quality rating, participation in Medicaid, staffing, COVID-related data.	CMS Medicare NH Compare Rating System.	Baseline.
	Resident characteristics	Age, race, sex, diagnoses, medication use, comorbidity, physical function, pain, vision, and dementia stage based on CDR.	Data extraction from medical records and MDS. CDR ratings will be measured via inputs from staff caregivers (e.g., nurse or CNAs).	
	Agitation, BPSD, affect, sleep & adverse effects	CMAI, NPI-NH, ARS, sleep & adverse events checklist.	Inputs from staff caregivers (e.g., nurse or CNAs) based on participants' conditions in past week.	Baseline & every two weeks.
Aims 1 & 2	Light level (lux & CS).	Lighting level each participant receives.	Personal light monitor, LYS button, every 10 minutes, 24 hours/day, 7 days/week.	
Aim 2	Light level (lux & CS).	Lighting level SABL delivers.	Manual on-site measurements.	Baseline & twice a week.
Aim 3	NH employee characteristics	Age, race, gender, education, & professional experiences.	Surveys.	Week 13.

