7.4 Test Article(s) (Study Drug(s) and/or Study Device(s))

7.4.1 Description

Provide a brief description of all test articles (drugs (including any foods and dietary supplements), devices and/or biologics) used in the research including the purpose of their use and their approval status with the Food and Drug Administration (FDA). Include information about the form of the drug product (e.g., tablets, capsules, liquid).

The SABL system has a pre-programmed 24-hour control schedule on illuminance settings to mimic the natural bright-dark cycle. While research evidence suggests the potential positive effect of the lighting intervention on people with dementia, the lighting device being used in this research is not currently FDA approved for the use of improving behavioral symptoms of dementia. It will regularly monitor the lighting level using customized photosensors and automatically adjust the lights to accommodate the daylight effect, minimizing staff burden and maintenance efforts, while maximizing the LI effect. Our proposed SABL will provide bright light with illuminance targeted at 400 lux and CS ≥ 0.3 at the eye level, and dim light ≤ 40 lux and low CS ≤ 0.1 at night to maintain a bright-dark cycle to regulate activity/rest rhythm, improve sleep, and reduce agitation. We will measure the light levels received by each participant using a personal, wearable lighting measure device, LYS button, and will use the actual dosage (lux and CS levels) received by participants to analyze the intervention effect.

The lighting intervention, SABL, design and installation will involve five phases:

1) **Developing an implementation protocol.** PIs [name] and [name] will set up an advisory board at each NH that includes a certified nursing assistant (CNA), a nurse, the director of nursing (DON), the director of maintenance (DOM), and the administrator (NHA). Through the advisory board, we will obtain input from NH stakeholders about implementation procedures. Next, we will develop a protocol that lists the workflow, key steps, and associated personnel customized to each facility. [name] will work with the DOM at each facility to finalize the plan for SABL installation and maintenance and to ensure the installation follows NH regulations.

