8.3 Statistical or Analytic Methods

Describe the statistical methods (or non-statistical methods of analysis) that will be employed.

Aim 1

All data will initially be assessed with descriptive techniques to determine distributions and identify outliers. Baseline to post-intervention changes in participants' CMAI, NPI-NH, and ARS scores will be used as the outcomes in all subsequent analyses. To conduct the group analysis, each participant will serve as their own control, which allows minimal use of control variables. The effect of the intervention will be analyzed using multi-level modeling to adjust for clustering of participants at the facility level. We will use the daytime and nighttime average of lighting dosages (lux and CS) from the personal light monitors as the independent variable to analyze the effect of SABL on changes in CMAI, NPI, and ARS. Although not powered for a detailed analysis, we will explore the impact of participant characteristics (sex, age, race, ethnicity, ADRD stage, and daylight exposure) on the intervention effect by adding them as covariates to the regression model.

Aim 2

All data will initially be assessed using descriptive techniques to examine underlying assumptions and detect any violations. To assess the intervention fidelity, the lux and CS data measured via manual measurements will be analyzed using one sample t-tests to analyze lighting levels during the day and nighttime, compared to the target levels. The data from personal light monitors will be analyzed similarly at individual level. Although not powered for a detailed analysis, we will explore the impact of participant characteristics (e.g., sex, age, race, dementia stage, comorbidity, facility, and daylight conditions) on the lighting received based on the personal light monitor.

Aim 3

Quantitative Analysis: The data include ratings of acceptability, feasibility, appropriateness, time, and cost of installing and maintaining the intervention. All data will be analyzed using descriptive analyses. Although not powered for a detailed analysis, we will explore differences in perceptions of intervention feasibility and acceptability between sexes as well as the difference across professional roles and between facilities.

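### Aim 2 tests light delivery with one-sample t-tests that have no tolerance or direction: for a point target such as 400 lux, non-significance cannot show delivery, and for floors and ceilings the compliant side is not specified

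*Protocol*

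**What the plan says.** Protocol 1.2 lists among the primary outcomes "fidelity of SABL (e.g., lighting level on site and at individual level". Section 7.1 says of Aim 2: "The actual lighting data will be compared to the intended SABL design". The method, in protocol 8.3 and repeated in the SAP, is that data from "manual measurements will be analyzed using one sample t-tests to analyze lighting levels during the day and nighttime, compared to the target levels". Monitor data are to be analysed in the same way at individual level. No tolerance, sidedness, significance level or success rule for Aim 2 appears in either document.

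The targets are written in different forms:

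- **Day illuminance:** 400 lux, written as a target value.
- **Day CS:** equal to 0.3 in 2.2, 7.1, Receipt of Test Article and Preparation and Dispensing, but a floor in 7.4.1 ("illuminance targeted at 400 lux and CS ≥ 0.3 at the eye level") and 7.4.2.
- **Night:** ceilings of 40 lux and CS 0.1.
- **Real-time alert (7.1):** wall sensors "can detect any problematic lighting events (e.g., <400lux or CS<0.3 during the day) in real-time", so the alert treats both day values as floors.

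Manual readings in 7.1 "will be performed by the research team twice a week during the intervention and control periods". Table 2 describes the quantity they measure as "Lighting level SABL delivers".

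**The concern.** A one-sample t-test takes the target as its null value. For a point target, the result the study hopes for is the null itself. A non-significant result can come from accurate delivery or from a few variable readings, and the test cannot tell these apart. The plan supplies no other rule by which the light could be called delivered.

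For a floor or ceiling, the same test does answer the question if it is read on the compliant side. A night mean significantly below 40 lux is good evidence about that mean; one significantly above is failure. By day the reading depends on whether the target is a point or a floor, and the documents give both for CS.

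At stake is the interpretation of a listed primary outcome. Fidelity also bears on Aim 1: if agitation does not change, the reader will want to know whether the light arrived as designed.

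**Working it through.** **The plan's own figure.** None exists for Aim 2. The only stated power (0.92, protocol 8.2) uses an effect size of d = 0.53 for the resident sample and has no bearing on this test.

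**Inputs**

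- Number of readings: 2 visits a week x 4 SABL weeks = 8 visit-level values per home; 16 if both homes are pooled as independent visits with no allowance for home.
- Target 400 lux; illustrative true mean 360 lux, a 40-lux (10%) shortfall (assumption).
- Two-sided alpha 0.05 (assumption; none is stated for Aim 2).
- SD between visit-level values under SABL: not given. Assumed 30, 40 and 60 lux. The only SDs in the documents are baseline values in Preparation and Dispensing, running from 91 to 123 lux (bedroom 105). They are shown as a second range. They may not apply to a sensor-controlled system, and may not be visit-level.

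**Step 1. Chance that the planned test misses the shortfall.** Noncentrality = 40 x sqrt(n) / SD. The result is non-significant when |t| < t(0.975, n-1), which is 2.365 for n = 8. Example: SD 40, n = 8 gives 40 x 2.828 / 40 = 2.83, power 0.681, so 0.319 non-significant.

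| SD (lux) | n = 8 | n = 16 |
|---|---|---|
| 30 | 10% | <1% |
| 40 | 32% | 4% |
| 60 | 63% | 30% |
| 91 | 81% | 62% |
| 105 | 85% | 70% |
| 123 | 87% | 77% |

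**Step 2. What an interval would report.** The 90% CI half-width is t(0.95, n-1) x SD / sqrt(n), with t = 1.895 at n = 8. For SD 40: 1.895 x 40 / 2.828 = 26.8 lux. For SD 30, 40 and 60, the half-width is about 20, 27 and 40 lux at n = 8, and 13, 18 and 26 lux at n = 16. At n = 8 and SD 91, 105 and 123 it is 61, 70 and 82 lux.

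**Step 3. How a tolerance rule would behave.** The rule is that the 90% CI must lie wholly within plus or minus 40 lux of target (40 is illustrative only). Simulation with 400,000 draws per cell:

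| SD (lux) | True mean on target: passes, n = 8 | n = 16 |
|---|---|---|
| 30 | 92% | >99% |
| 40 | 63% | 97% |
| 60 | 17% | 63% |
| 91 | 1.8% | 11% |
| 105 | 0.7% | 4% |
| 123 | 0.2% | 1% |

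A true 40-lux shortfall passes about 5% of the time or less in every cell. The rule therefore controls false claims of delivery, which the planned test does not, but with few variable readings it seldom confirms true delivery.

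**The case against.** The strongest reply is that this is a pilot. Aim 2 promises to evaluate and compare, not to pass or fail; descriptive analysis comes first; and a one-sample t-test normally comes with the mean, its sign and an interval. On that view the remedy is mostly a matter of reporting. This has force and limits the severity, but fidelity is a listed primary outcome and the t-test is the only inferential method stated for it.

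Four stronger readings are tempting, and the documents do not support them:

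- **That the test can never show delivery.** At the night ceilings it can. If the true night mean were 30 lux, 8 readings with an assumed SD of 10 or 15 lux would show it below 40 lux 68% or 37% of the time with the two-sided test, and 82% or 52% with a one-sided 95% limit. These are correct detections of compliance, not false alarms.
- **That the sponsor intends to treat non-significance as success.** Neither document says so. The gap is that no other rule is given.
- **That no delivery criterion exists anywhere.** The alert in 7.1 is one, but it is an operational trigger and is not carried into the analysis.
- **That the monitor unit is undefined.** Aim 1 in both documents names daytime and nighttime averages from the monitors, and one of each per resident is the natural reading at individual level. The unit is unstated only for the manual readings.

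**Conclusion.** The point holds in a limited form. For a target written as a point, the planned test can show departure, but its non-significance cannot show delivery. That is a matter of logic and rests on no assumed number. Its practical size does rest on assumptions. At one home with 8 visit-level readings, a 40-lux shortfall would go undetected 10% to 63% of the time over SDs of 30 to 60 lux, and 81% to 87% if the baseline SDs applied. For targets written as bounds the test is usable, but only one-sided in the compliant direction, which the plan should state. The change is recommended before analysis; nothing here invalidates the data to be collected.

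**What to change.** Amend the Aim 2 text in protocol 8.3 and the SAP as follows:

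1. Restrict the fidelity analysis to SABL-on weeks.
2. Make the main report mean minus target with a 90% CI, shown by home. Use visit-level values for manual readings, and one daytime and one nighttime average per resident for monitors.
3. State for each target whether it is a point, a floor or a ceiling. Judge a point against a tolerance set in advance by the study team, and a bound by a one-sided 95% limit. If 400 lux is declared a floor, it needs a tolerance too: a system centred exactly on 400 would clear a strict one-sided limit only 5% of the time. Keep any pass/fail reading secondary.
4. From the monitors, also report hours per day at target against the protocol's own estimate of at least 4 hours (7.4.2). Exposure hours are already to be calculated under Subject Compliance Monitoring.
5. Reconcile the passages giving day CS as equal to 0.3 with those giving it as a floor, and both with the alert rule. This review does not choose a light level.

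The cost is wording and one advance decision on tolerance; no new measurements are needed. The downside is that a positive fidelity claim becomes harder to reach. With the illustrative 40-lux tolerance and 8 readings, on-target delivery passes 92%, 63% or 17% of the time at SDs of 30, 40 or 60 lux, and about 2% or less at 91 to 123 lux. That is why the estimate and its interval should lead.

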9.0 Data and Safety Monitoring Plan

This section is required when research involves more than Minimal Risk to subjects as defined in "HRP-001 SOP- Definitions."

Minimal Risk is defined as the probability and magnitude of harm or discomfort anticipated in the research that are not greater in and of themselves than those ordinarily encountered in daily life or during the performance of routine physical or psychological examinations or tests. For research involving prisoners, Minimal Risk is the probability and magnitude of physical or psychological harm that is normally encountered in the daily lives, or in the routine medical, dental, or psychological examination of healthy persons.

Please complete each section below if the research involves more than minimal risk to subjects or indicate not applicable.

[Do not type here]

9.1 Periodic evaluation of data

Describe the plan to periodically evaluate the data collected regarding both harms and benefits to determine whether subjects remain safe.

Not applicable.

9.2 Data that are reviewed

Describe the data that are reviewed, including safety data, untoward events, and efficacy data.

Not applicable.

